### **Subgroup analysis of primary endpoint**

The primary efficacy endpoint will also be analysed for the pre-specified subgroups as specified in Section 4.4.5. The analyses for the subgroup population will be performed with the primary Estimand (Estimand 1) for the primary endpoint regarding the intercurrent events and missing data handling, and population level summary. In each subgroup, the treatment effects for the primary endpoint will be provided, as well as the corresponding 95% CI.

Interaction effects will be tested using the ANCOVA model between treatment arms and subgroup factor. The model will include all the covariates in the main statistical model plus the subgroup variable and the subgroup-by-treatment interaction. A p-value for the test of interaction will be provided.

Forest plot will be provided to present the estimates and the corresponding 95% CI for each subgroup.

### **Multiplicity control**

## **8.2 Analysis of Key Secondary Efficacy Endpoints**

The key secondary efficacy endpoints for the study are:

- Percentage change from baseline in EASI at Day 169 (Week 24).
- Percentage of patients with at least a 75% reduction from baseline in EASI (EASI 75) at Days 113 (Week 16) and Day 169 (Week 24).
- Percentage of patients with a response of IGA 0 or 1 and a reduction from baseline of  $\geq 2$  points at Days 113 (Week 16) and Day 169 (Week 24).
- Proportion of patients with improvement (reduction) of weekly average of pruritus NRS  $\geq 4$  with a baseline pruritus NRS of  $\geq 4$  from baseline to Days 113 (Week 16) and Day 169 (Week 24).

### **Analysis for continuous key secondary endpoint**

Below Estimands will be applied to analyze the continuous key secondary endpoint: Percentage change from baseline in EASI at Day 169 (Week 24). Please refer the details in Section 15.1 in Appendices. For analysis approach with multiple imputation, same multiple imputation process described for primary endpoint will be applied for the continuous key secondary endpoint.

- Estimand 4a description: The mean difference in percentage change from baseline in EASI to Day 169 (Week 24) of 4 different KY1005 dosing regimens compared to placebo, [REDACTED] in adult patients with moderate to severe AD who have had inadequate response to topical treatments or inadvisability of topical treatment.

The analysis of the key secondary endpoint and the handling of intercurrent events and missing data will be performed similar to Estimand 1 (Table 3 Estimands and Strategies for Managing Intercurrent Events for Primary Endpoint **Table 3**, Column 2).

- Estimand 4b description: The mean difference in percentage change from baseline in EASI to Day 169 (Week 24) of 4 different KY1005 dosing regimens compared to placebo, [REDACTED] in adult patients with moderate to severe AD who have had inadequate response to topical treatments or inadvisability of topical treatment.

The analysis of the key secondary endpoint and the handling of intercurrent events and missing data will be performed similar to Estimand 2 (Table 3 Estimands and Strategies for Managing Intercurrent Events for Primary Endpoint **Table 3**, Column 3).

[figure not shown]
- Estimand 4c description: The mean difference in percentage change from baseline in EASI to Day 169 (Week 24) of 4 different KY1005 dosing regimens compared to placebo, [REDACTED] in adult patients with moderate to severe AD who have had inadequate response to topical treatments or inadvisability of topical treatment.

[figure not shown]
The analysis of the key secondary endpoint and the handling of intercurrent events and missing data will be performed similar to Estimand 3 (Table 3 Estimands and Strategies for Managing Intercurrent Events for Primary Endpoint **Table 3**, Column 4).

### **Analysis for binary key secondary endpoints**

#### **Table 4 Estimands and Strategies for Managing Intercurrent Events for Binary Key Secondary Endpoint**

[REDACTED]
------------

- 
- Estimand 5c description: The Proportion of patients with EASI 75 at Day 169 (Week 24) for different KY1005 dosing regimens compared to placebo, [REDACTED] in adult patients with moderate to severe AD who have had inadequate response to topical treatments or inadvisability of topical treatment. The analysis of the key secondary endpoint and the handling of intercurrent events and missing data will be performed similar to Estimand 5a (Table 4, Column 1).
  - Estimand 5d description: The Proportion of patients with EASI 75 at Day 169 (Week 24) for different KY1005 dosing regimens compared to placebo, [REDACTED] in adult patients with moderate to severe AD who have had inadequate response to topical treatments or inadvisability of topical treatment. The analysis of the key secondary endpoint and the handling of intercurrent events and missing data will be performed similar to Estimand 5b (Table 4 Column 2).
  - Estimand 6a description: The Proportion of patients with IGA 0/1 and a reduction from baseline of  $\geq 2$  points at Day 113 (Week 16) for 4 different KY1005 dosing regimens compared to placebo, [REDACTED] in adult patients with moderate to severe AD who have had inadequate response to topical treatments or inadvisability of topical treatment. The analysis of the key secondary endpoint and the handling of intercurrent events and missing data will be performed similar to Estimand 5a (Table 4, Column 1).
  - Estimand 6b description: The Proportion of patients with IGA 0/1 and a reduction from baseline of  $\geq 2$  points at Day 113 (Week 16) for 4 different KY1005 dosing regimens compared to placebo, [REDACTED] in adult patients with moderate to severe AD who have had inadequate response to topical treatments or inadvisability of topical treatment. The analysis of the key secondary endpoint and the handling of intercurrent events and missing data will be performed similar to Estimand 5b (Table 4, Column 2).
  - Estimand 6c description: The Proportion of patients with IGA 0/1 and a reduction from baseline of  $\geq 2$  points at Day 169 (Week 24) for different KY1005 dosing regimens compared to placebo, [REDACTED] in adult patients with moderate to severe AD who have had inadequate response to topical treatments or inadvisability of topical treatment. The analysis of the key secondary endpoint and the handling of intercurrent events and missing data will be performed similar to Estimand 5a (Table 4, Column 1).
  - Estimand 6d description: The Proportion of patients with IGA 0/1 and a reduction from baseline of  $\geq 2$  points at Day 169 (Week 24) for different KY1005 dosing regimens compared to placebo,

[REDACTED]  
[REDACTED] in adult patients with moderate to severe AD who have had inadequate response to topical treatments or inadvisability of topical treatment. The analysis of the key secondary endpoint and the handling of intercurrent events and missing data will be performed similar to Estimand 5b (Table 4, Column 2).

- Estimand 7a description: The Proportion of patients with improvement of weekly average of pruritus NRS  $\geq 4$  from baseline at Day 113 (Week 16) for 4 different KY1005 dosing regimens compared to placebo, [REDACTED] in adult patients with moderate to severe AD who have had inadequate response to topical treatments or inadvisability of topical treatment. The analysis of the key secondary endpoint and the handling of intercurrent events and missing data will be performed similar to Estimand 5a (Table 4, Column 1).
- Estimand 7b description: The Proportion of patients with improvement of weekly average of pruritus NRS  $\geq 4$  from baseline at Day 113 (Week 16) for 4 different KY1005 dosing regimens compared to placebo, [REDACTED] in adult patients with moderate to severe AD who have had inadequate response to topical treatments or inadvisability of topical treatment. The analysis of the key secondary endpoint and the handling of intercurrent events and missing data will be performed similar to Estimand 5b (Table 4, Column 2).
- Estimand 7c description: The Proportion of patients with improvement of weekly average of pruritus NRS  $\geq 4$  from baseline at Day 169 (Week 24) for different KY1005 dosing regimens compared to placebo, [REDACTED] in adult patients with moderate to severe AD who have had inadequate response to topical treatments or inadvisability of topical treatment. The analysis of the key secondary endpoint and the handling of intercurrent events and missing data will be performed similar to Estimand 5a (Table 4, Column 1).
- Estimand 7d description: The Proportion of patients with improvement of weekly average of pruritus NRS  $\geq 4$  from baseline at Day 169 (Week 24) for different KY1005 dosing regimens compared to placebo, [REDACTED] in adult patients with moderate to severe AD who have had inadequate response to topical treatments or inadvisability of topical treatment. The analysis of the key secondary endpoint and the handling of intercurrent events and missing data will be performed similar to Estimand 5b (Table 4, Column 2).

Summary of binary key secondary efficacy endpoints at scheduled visits will be provided. Bar plots will be provided. Further details please refer to Section 8.3.

### **Subgroup analysis of key secondary endpoints**

The following key secondary efficacy endpoints will also be analysed for subgroups analysis, using the same subgroups as for primary efficacy endpoint.

- Percentage of patients with at least a 75% reduction from baseline in EASI (EASI 75) at Days 113 (Week 16).
- Percentage of patients with a response of IGA 0 or 1 and a reduction from baseline of  $\geq 2$  points at Days 113 (Week 16).

The analyses for the subgroup population will be performed using primary Estimand for the corresponding key secondary endpoint (Estimand 5a, 6a respectively). Forest plots will be provided to present the estimates and the corresponding 95% CI for each subgroup.

### 8.3 Analysis of Other Secondary Efficacy Endpoints

Below are the additional other secondary efficacy endpoints for the study:

- Absolute change from baseline in EASI at Days 15 (Week 2), 29 (Week 4), 57 (Week 8), 85 (Week 12), 113 (Week 16), 141 (Week 20) and 169 (Week 24).
- Percentage change from baseline in EASI at Days 15 (Week 2); 29 (Week 4), 57 (Week 8), 85 (Week 12) and 141 (Week 20).
- Percentage of patients with at least a 50% reduction from baseline in EASI (EASI 50) at Days 15 (Week 2), 29 (Week 4), 57 (Week 8), 85 (Week 12), 113 (Week 16), 141 (Week 20) and 169 (Week 24).
- Percentage of patients with at least a 75% reduction from baseline in EASI (EASI 75) at Days 15 (Week 2), 29 (Week 4), 57 (Week 8), 85 (Week 12) and 141 (Week 20).
- Percentage of patients with at least a 90% reduction from baseline in EASI (EASI 90) at Days 15 (Week 2), 29 (Week 4), 57 (Week 8), 85 (Week 12), 113 (Week 16), 141 (Week 20) and 169 (Week 24).
- Percentage of patients with a 100% reduction from baseline in EASI (EASI 100) at Days 15 (Week 2), 29 (Week 4), 57 (Week 8), 85 (Week 12), 113 (Week 16), 141 (Week 20) and 169 (Week 24).
- Change in IGA from baseline to Day 169 (Week 24) and over time.
- Percentage of patients with a response of IGA 0 or 1 and a reduction from Baseline of  $\geq 2$  points at Days 15 (Week 2), 29 (Week 4), 57 (Week 8), 85 (Week 12) and 141 (Week 20).
- Absolute and percentage change in SCORAD Index from baseline to Day 169 (Week 24) and over time.
- Absolute and Percentage change in affected BSA from baseline to Day 169 (Week 24) and over time.
- Absolute and Percentage change in POEM from baseline to Day 169 (Week 24) and over time.
- Absolute and Percentage change in DLQI from baseline to Day 169 (Week 24) and over time.
- Absolute and Percentage change in ADCT from baseline to Day 169 (Week 24) and over time.
- Absolute and Percentage change in HADS from baseline to Day 169 (Week 24) and over time.
- Absolute and Percentage change in weekly average of pruritus NRS from baseline to Day 169 (Week 24) and over time.

- Proportion of patients with improvement (reduction) of weekly average of pruritus NRS  $\geq 3$  with a baseline pruritus NRS of  $\geq 3$  from baseline to Days 113 (Week 16) and 169 (Week 24).
- Time to loss of EASI 75 in patients randomized to withdrawal post-Week 24.
- Time to loss of IGA 0/1 in patients randomized to withdrawal post-Week 24.
- Time to loss of EASI 50 in patients randomized to withdrawal post-Week 24.

The analysis of the additional secondary endpoints analysis will be performed using the FAS set.

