An overall test for the treatment effect of KY1005 will be conducted. For each treatment regimen and all efficacy variables, the analysis will be comparisons of each of the KY1005 treatment groups with the Placebo group. For the primary endpoint, the overall type I error rate will be controlled using a hierarchical testing procedure across the four dose regimens against placebo. For each secondary endpoint analyzed, the same multiplicity adjustment approach will be applied as for the primary endpoint. No multiplicity adjustment will be made across the endpoints.

1-Mar-2022

Version number: 1

For the continuous endpoints: An analysis of covariance (ANCOVA) model will be used. This model includes treatment, randomisation strata (region, disease severity) as fixed effects, and baseline value as a covariate.

A mixed-effect model with repeated measures will be used as a sensitivity analysis for primary and continuous key secondary endpoints. This model includes the factors (fixed effects) for treatment, randomisation strata (region, disease severity), visit, treatment-by-visit interaction, and relevant baseline value.

For the categorical endpoints: Cochran-Mantel-Haenszel test stratified by randomisation strata (region, disease severity) will be used at each analysis timepoint.

Data will be presented graphically, where applicable, and with summary statistics by visit and by treatment regimen.

Safety Analyses:

Adverse events will be coded using the Medical Dictionary for Regulatory Activities (MedDRA, latest version) and will be summarised in incidence tables by System Organ Class and Preferred Term, and by treatment regimen. Adverse events will be further summarised by maximum severity and relationship to study medication. Concomitant medications will be coded using the World Health Organization Drug Dictionary and will be summarised in incidence tables by Drug Class and Preferred name, and by treatment regimen.

Other routine safety assessments such as vital signs, 12-lead ECG and safety laboratory tests will be summarised by treatment regimen using statistics for continuous or categorical data, as appropriate.

Pharmacokinetic Analyses:

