10.4.2.2 Secondary Analysis

The key secondary efficacy endpoints for the study are:

- Percentage change from Baseline in EASI at Day 169 (Week 24).
- Percentage of patients with at least a 75% reduction from Baseline in EASI (EASI 75) at Days 113 (Week 16) and 169 (Week 24).
- Percentage of patients with a response of IGA 0 or 1 and a reduction from Baseline of ≥2 points at Days 113 (Week 16) and 169 (Week 24).
- Proportion of patients with improvement (reduction) of weekly average of pruritus NRS ≥4 with a Baseline pruritis NRS of ≥4 from Baseline to Days 113 (Week 16) and 169 (Week 24).

Additional secondary efficacy endpoints for the study are:

- Absolute change from Baseline in EASI at Days 15 (Week 2), 29 (Week 4),
 57 (Week 8), 85 (Week 12), 113 (Week 16), 141 (Week 20) and 169 (Week 24).
- Percentage change from Baseline in EASI at Days 15 (Week 2), 29 (Week 4), 57 (Week 8), 85 (Week 12) and 141 (Week 20).
- Percentage of patients with at least a 50% reduction from Baseline in EASI (EASI 50) at Days 15 (Week 2), 29 (Week 4), 57 (Week 8), 85 (Week 12), 113 (Week 16), 141 (Week 20) and 169 (Week 24).
- Percentage of patients with at least a 75% reduction from Baseline in EASI (EASI 75) at Days 15 (Week 2), 29 (Week 4), 57 (Week 8), 85 (Week 12) and 141 (Week 20).
- Percentage of patients with at least a 90% reduction from Baseline in EASI (EASI 90) at Days 15 (Week 2), 29 (Week 4), 57 (Week 8), 85 (Week 12), 113 (Week 16), 141 (Week 20) and 169 (Week 24).
- Percentage of patients with a 100% reduction from Baseline in EASI (EASI 100) at Days 15 (Week 2), 29 (Week 4), 57 (Week 8), 85 (Week 12), 113 (Week 16), 141 (Week 20) and 169 (Week 24).
- Change in IGA from Baseline to Day 113 (Week 16) and over time.
- Percentage of patients with a response of IGA 0 or 1 and a reduction from Baseline of ≥2 points at Days 15 (Week 2), 29 (Week 4), 57 (Week 8), 85 (Week 12) and 141 (Week 20).
- Absolute and percentage change in SCORAD Index from Baseline to Day 169 (Week 24) and over time.
- Absolute and Percentage change in affected BSA from Baseline to Day 169 (Week 24) and over time.
- Absolute and Percentage change in POEM from Baseline to Day 169 (Week 24) and over time.
- Absolute and Percentage change in DLQI from Baseline to Day 169 (Week 24) and over time.

• Absolute and Percentage change in ADCT from Baseline to Day 169 (Week 24) and over time.

1-Mar-2022

Version number: 1

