17.8 Appendix 8 - Hospital Anxiety and Depression Scale

1-Mar-2022

Version number: 1

		Hospital Anxiety and	n accecement					
		Depression Scale (HADS)						
		Name:	Date:					
	ERE	Clinicians are aware that emotions play an important these feelings he or she will be able to help you more		FOLD HERE				
	FOLD HERE	This questionnaire is designed to help your clinician to know how you feel. Read each item below and underline the reply which comes closest to how you have been feeling in the past week. Ignore the numbers printed at the edge of the questionnaire.						
		Don't take too long over your replies, your immediate accurate than a long, thought-out response.	e reaction to each item will probably be more					
1	D			A]			
		I feel tense or 'wound up' Most of the time	I feel as if I am slowed down Nearly all the time					
		A lot of the time	Very often					
		From time to time, occasionally Not at all	Sometimes Not at all					
		I still enjoy the things I used to enjoy	I get a sort of frightened feeling like					
	0	Definitely as much	'butterflies' in the stomach					
	1 2	Not quite so much Only a little	Not at all Occasionally	0				
	3	Hardly at all	Quite often	2				
		I get a sort of frightened feeling as if	Very often	3				
		something awful is about to happen Very definitely and quite badly	I have lost interest in my appearance Definitely					
		Yes, but not too badly	I don't take as much care as I should					
		A little, but it doesn't worry me	I may not take quite as much care I take just as much care as ever					
		Not at all I can laugh and see the funny side of things	I feel restless as if I have to be on the move					
	0	As much as I always could	Very much indeed	3				
	1 2	Not quite so much now Definitely not so much now	Quite a lot Not very much	2				
	3	Not at all	Not at all	0				
		Worrying thoughts go through my mind	I look forward with enjoyment to things					
		A great deal of the time A lot of the time	As much as I ever did Rather less than I used to					
		Not too often	Definitely less than I used to					
		Very little	Hardly at all					
	3	I feel cheerful Never	I get sudden feelings of panic Very often indeed	3				
	2	Not often	Quite often	2				
	1	Sometimes Most of the time	Not very often Not at all	1				
	U	I can sit at ease and feel relaxed	I can enjoy a good book or radio or					
		Definitely	television programme					
		Usually	Often Sometimes					
		Not often Not at all	Not often					
		Non-abach that one boom	Very seldom					

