#### 9. Hospital Anxiety and Depression Scale

The HADS is a validated 14-item PRO measure used to assess states of anxiety and depression over the past week. This will be completed using an internet enabled device. Only the HADS total score will be presented in the analysis

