#### **Analysis of other continuous secondary endpoints**

For each of the other continuous secondary endpoint, the following by visit summary tables will be provided.

- Summary table at each scheduled visit up to Week 24 [REDACTED]  
[REDACTED]  
[REDACTED]  
[REDACTED]  
[REDACTED] Mean difference with 95% CI and p-value will be provided.
- Summary table at each scheduled visit up to Week 24 [REDACTED]  
[REDACTED]
- Summary table at each scheduled visits from Week 24 onwards, [REDACTED]  
[REDACTED]  
[REDACTED]  
[REDACTED]  
[REDACTED] The change value (or percent change value) is calculated using Week 0 baseline value. Summary is presented using Week 24 re-randomization treatment arms.
- Summary table at each scheduled visits from baseline to Week 52, [REDACTED]  
[REDACTED]  
[REDACTED]  
[REDACTED]  
[REDACTED] The change value (or percent change value) is calculated using Week 0 baseline value. Summary is presented using Week 24 re-randomization treatment arms.
- Summary table at each scheduled visit from Week 24 onwards, [REDACTED]  
[REDACTED]  
[REDACTED] The change value (or percent change value) is calculated using Week 0 baseline value. Summary is presented using Week 24 re-randomization treatment arms.
- Summary table at each scheduled visit from baseline up to Week 52, [REDACTED]  
[REDACTED]  
[REDACTED] The change value (or percent change value) is calculated using Week 0 baseline value. Summary is presented using Week 24 re-randomization treatment arms.

[Redacted]

For each of the other continuous secondary endpoint, the following line plots will be provided:

- Line plot will be provided including scheduled visits up to Week 24 using the LSMEAN estimation from the above by visit summary table.
- Line plot will be provided including scheduled visits from Week 24 up to Week 52 among patients in Part 2 using the mean change (or percent change) estimation from the above by visit summary table [Redacted]. The change value (or percent change value) is calculated using Week 0 baseline value. The line plot will be presented using Week 24 re-randomization treatment arms.
- Line plot will be provided including scheduled visits from baseline up to Week 52 among patients in Part 2 using the mean change (or percent change) estimation from the above by visit summary table [Redacted]. The change value (or percent change value) is calculated using Week 0 baseline value. The line plot will be presented using Week 24 re-randomization treatment arms .

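### Percentage change in HADS total is planned with a p-value although the score can be 0 at baseline and has no entry threshold; absolute change should be the only tested HADS measure

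*SAP*

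**What the plan says.** SAP 8.3 lists "Absolute and Percentage change in HADS from baseline to Day 169 (Week 24) and over time" as an other secondary endpoint. Protocol 10.4.2.2 has the same item.

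On the scale, SAP 4.4.8 states: "The HADS is a validated 14-item PRO measure used to assess states of anxiety and depression over the past week". It adds: "Only the HADS total score will be presented in the analysis".

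On the analysis, SAP 8.3 states: "For each of the other continuous secondary endpoint, the following by visit summary tables will be provided". For the table up to Week 24: "Mean difference with 95% CI and p-value will be provided". Later items in the same list mention percentage change explicitly, so it falls within their scope. SAP 8.3 places these endpoints on the full analysis set, which is all randomised patients (Protocol 10.3.1, SAP 4.3.2). For continuous endpoints Protocol 10.4.2 specifies ANCOVA: "This model includes treatment, randomisation strata (region, disease severity) as fixed effects, and baseline value as a covariate".

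SAP section 4 defines percentage change as 100 times the change divided by the baseline value. The visible text has no rule for a baseline of 0.

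**The concern.** Percentage change works for EASI, affected BSA and pruritus NRS because Protocol 4.2 sets baseline minima of 16, 10% and 4. Nothing comparable exists for HADS. The printed item scores on the form in Protocol Appendix 8 start at 0 (the answer "Definitely as much" scores 0), so a patient with severe skin disease but no anxiety or depression can have a total of 0, 1 or 2.

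Two things follow. A patient at 0 has no percentage change, so as visibly written the endpoint cannot be computed on its stated analysis set. A patient at 1 to 3 can contribute a very large positive value for a trivial change, whereas nobody can fall below -100%. A mean difference on this variable gives most weight to the patients for whom HADS matters least. It also puts a second p-value beside the one for absolute change on the same scale, and the two may disagree.

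**Working it through.** **Inputs from the documents.** Percentage change = 100 × C / B, with C the change and B the baseline (SAP section 4). HADS has 14 items; the form prints item scores from 0 to 3, so the total runs from 0 to 14 × 3 = 42. There is no HADS entry criterion (Protocol 4.2). There are 70 patients per arm, 350 in all. Tests are two-sided at 5% (SAP section 4), with ANCOVA adjusting for baseline.

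**The plan's own figure.** There is none for HADS. The only stated power is at least 84% for percentage change in EASI (Protocol synopsis). At 70 per arm that corresponds to a standardised difference of 0.503, which says nothing about HADS.

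**Step 1: the formula.** A 3-point rise is 300/B per cent. The largest possible rise is 100 × (42 - B)/B, and the largest fall is always -100%.

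| Baseline B | 3-point rise | Largest possible rise |
|---|---|---|
| 0 | undefined | undefined |
| 1 | +300% | +4100% |
| 2 | +150% | +2000% |
| 4 | +75% | +950% |
| 10 | +30% | +320% |
| 20 | +15% | +110% |

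This step needs no assumption.

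**Step 2: how often baseline is 0 (assumed distribution).** For a negative binomial with mean m and SD s, P(0) = (m/s²)^(m²/(s² - m)).

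- 8 and 6: (8/36)^(64/28) = 3.2%, about 11 of 350
- 10 and 7: (10/49)^(100/39) = 1.7%, about 6 of 350
- 13 and 7: (13/49)^(169/36) = 0.2%, about 1 of 350
- 16 and 7: (16/49)^(256/33) = 0.02%, effectively none

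**Step 3: power (assumed model).** Follow-up = baseline × (0.9 - 0.2 × active) + 1 + noise, rounded and limited to 0 to 42, with 70 per arm and no dropout. The test is ANCOVA on treatment and baseline. Patients at baseline 0 are left out of the percentage analysis only. Noise is either constant (SD 3) or has variance proportional to baseline; the latter was run with and without the added 1 point.

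| Baseline mean/SD | Absolute, constant noise | Percentage, constant noise | Percentage, scaled noise (with / without +1) |
|---|---|---|---|
| 8/6 | 88% | 28% | 59% / 65% |
| 10/7 | 97% | 39% | 75% / 83% |
| 13/7 | >99% | 77% | 98% / 98.5% |
| 16/7 | >99% | 97% | >99% / >99% |

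Absolute change stayed between 86% and over 99% under both noise models. Percentage change was never the more powerful. With constant noise, patients at baseline 1 to 3 carried 76%, 68% and 38% of the variance of percentage change in the first three rows.

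**Step 4: a second, separate set of assumptions.** Baseline means were 6 to 15 with dispersion 1.5 to 5 (12 scenarios), constant noise SD 4, and an average benefit of 2 points proportional to baseline. Power was 80% to 85% on absolute change and 14% to 41% on percentage change. Baseline 0 occurred in 0.1% to 8.9%. Patients at baseline 1 to 3 were 3% to 35% of those analysed and carried 31% to 83% of the variance. The placebo mean percentage change was +3% to +25% while the median was about -2% to -3%.

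**The case against.** The best defence is that the plan already contains the remedy: the same bullet includes absolute change, which is defined for everyone. HADS is one of many other secondary measures, no decision rests on it, and the Protocol synopsis makes no multiplicity adjustment across endpoints. That stands, and it limits the harm.

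The size also depends heavily on assumptions that the documents neither support nor exclude. Giving a patient at baseline 1 the same noise as one at 20 produces large percentages almost by construction. Scaled noise or a higher baseline removes most of the loss. That stands too.

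A reader might infer more than the documents support:

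- **That the plan drops patients at baseline 0.** No such rule is visible. Parts of SAP 8.3 and the estimand tables are redacted and could hold one. It would settle the undefined values, though not the inflation at 1 to 3 unless it also changed how low baselines are handled.
- **That a real HADS benefit would be missed or reversed.** Absolute change is reported alongside. With constant noise the percentage estimate had the wrong sign in about 10%, 6% and 0.3% of trials for baseline means 8, 10 and 13, and the wrong sign with p < 0.05 in at most about 0.1%.
- **That the result depends mostly on nearly symptom-free patients.** Patients at baseline 2 or less carried 66%, 57% and 27% of the variance in those settings, so this is true only if baselines are low.
- **That DLQI, ADCT and POEM need the same change.** Percentage change is planned for them too (for example "Absolute and Percentage change in DLQI from Baseline to Day 169 (Week 24) and over time"), and they also start at 0 without an entry minimum. But entry requires pruritus NRS of at least 4 and each form asks about itch or symptoms over the last week, so totals near 0 are unlikely. Nothing was computed for them.

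**Conclusion.** The point holds as a limited one. From the text alone, percentage change in HADS is planned with a mean difference and p-value, is undefined at a baseline that the scale allows, and has no visible rule for that case. It is also asymmetric in a way that inflates small changes at low baselines. Absolute change, planned beside it, does not have these faults.

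How much this costs is unknown, because it depends on the HADS baseline distribution and on how noise varies with baseline. Over assumed baseline means of 8 to 16 the loss of power ranges from severe (28% against 88%) to negligible (both over 99%), and the second set of assumptions gives 14% to 41% against 80% to 85%. These figures assume complete data. Protocol 3.6 expects 49 of 70 patients per arm to complete, so power on either measure could be lower in practice. The primary and key secondary endpoints are unaffected.

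**What to change.** In SAP 8.3, state that absolute change is the only tested HADS measure. Show percentage change in HADS descriptively (median and interquartile range, no p-value) among patients with baseline above 0, and report the number excluded.

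This needs a few lines in the SAP and removes one set of p-values; data collection, sample size and the main analyses do not change. The downside is that there is no tested percentage figure for HADS to set beside the one for EASI.

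The endpoint wording can stay. If it is changed at the next protocol amendment, align the Protocol synopsis, 2.1.2 and 10.4.2.2 and SAP 2.2 together; that is a protocol change and not only a SAP edit. Treating DLQI, ADCT or POEM in the same way is optional and was not shown to be needed.
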